10.4	Protocol Amendment History	61
11	References	63

12	APPENDIX I Nonsignificant Risk Determination.....	65
13	APPENDIX II Device Labeling.....	70

STATEMENT OF COMPLIANCE

This non-significant risk (NSR) device study will be carried out in accordance with *Clinical Investigation of Medical Devices for Human Subjects – Good Clinical Practice* (ISO 14155 Third edition 2020-07) and the following:

- United States (US) Code of Federal Regulations (CFR) applicable to NSR device studies (21 CFR Part 50, 21 CFR Part 56, 21 CFR Part 812.2(b))

The protocol, informed consent form (ICF), recruitment materials, and all subject materials will be submitted to the Institutional Review Board (IRB) for review and approval. Approval of both the protocol and the consent form must be obtained before any subject is enrolled. Any amendment to the protocol will require review and approval by the IRB before the changes are implemented to the study. In addition, all changes to the consent form will be IRB-approved; a determination will be made regarding whether a new consent needs to be obtained from subjects who provided consent using a previously approved consent form.

1 PROTOCOL SUMMARY

1.1 SYNOPSIS

Title: Self-Fitting (SF) Strategy Validation NSR Device Study Protocol: **SF Study**

Study Description: A prospective, randomized controlled, adaptive design, non-inferiority, pre-market and NSR device study. To be conducted in a minimum of 28 adult subjects with mild-to-moderate hearing loss to validate the effectiveness of the *Vibe SF* strategy. Validation measures subject's perceived hearing aid benefit when using the *Vibe SF* self-fit hearing aids and when using Silk 1X Hearing Care Professional (HCP) fit hearing aids.

The study begins with a cross-over design. At the interim analysis, the possibility of an interaction effect is evaluated through a nuisance parameter. If it is determined to be likely, the design is switched to a parallel-group design with a larger sample size. Only data from the first period will be included from those subjects who early on participated in the cross-over design.

The Silk 1X HCP fit hearing aids are fitted to National Acoustic Laboratories Nonlinear Version 2 (NAL-NL2) prescriptive targets, verified by probe-mic real-ear measures (REM). The null hypothesis (H_0) is that subject's perceived hearing aids benefit using *Vibe SF* hearing aids is inferior to Silk 1X HCP fit hearing aids, and the alternative hypothesis (H_a) is that subject's perceived hearing aids benefit using *Vibe SF* hearing aids is non-inferior to that using Silk 1X HCP fit hearing aids.

Description of Study**Intervention:**

The mechanism for validating the *Vibe SF* strategy will be to compare subject's perceived hearing aid benefit after two 14 days series of using *Vibe SF*/Silk 1X HCP fit hearing aids.

Objectives:**Primary Effectiveness Objective:**

To demonstrate that the *Vibe SF* strategy is non-inferior to the HCP fit strategy in subject's perceived hearing aid benefit after using the *Vibe SF* and Silk 1X HCP fit hearing aids in real-life conditions.

Secondary Hearing Aid Benefit Objectives:

To score each of the following hearing aid benefit performance measures when the subject is using the *Vibe SF* and Silk 1X HCP fit hearing aids:

1. Sound quality, speech understanding and hearing aid satisfaction real-time assessment,
2. Speech-in-noise recognition performance, and
3. Hearing disability in communication situations.

Secondary Gain Selection Objective:

Individual frequency-specific real-ear gain comparison of the two different fitting strategies (*Vibe SF* and HCP fit).

Secondary Preference Objective:

Fitting strategy (*Vibe SF* or HCP fit) preference reported by the subject.

Secondary Safety Objective:

To estimate the rate of adverse device effects (ADEs) when the subject is using the *Vibe SF* hearing aids.

Endpoints:**Primary Effectiveness Endpoint:**

Differences in the benefit scores on each of the three communication subscales as captured by the Abbreviated Profile of Hearing Aid Benefit (APHAB) after wearing each *Vibe SF* / Silk 1X HCP fit hearing aids for 14 days. For each subject, the endpoints are the individual 3 communication subscale differences between the HCP fit subscale (benefit) score and SF subscale (benefit) score:

- $\Delta EC(benefit)_{HCP\ fit} - \Delta EC(benefit)_{SF}$
- $\Delta BN(benefit)_{HCP\ fit} - \Delta BN(benefit)_{SF}$
- $\Delta RV(benefit)_{HCP\ fit} - \Delta RV(benefit)_{SF}$

Secondary Hearing Aid Benefit Endpoints:

1. The subject's sound quality, speech understanding and hearing aid satisfaction Ecological Momentary Assessment (EMA) ratings measured repeatedly under real-life conditions,
2. Speech-in-noise recognition performance as measured by the Quick Speech-In-Noise test (QuickSIN),
3. Hearing disability resulting from hearing loss quantified by the short form of the Speech, Spatial, and Qualities of Hearing Scale for clinical use: the SSQ-12 questionnaire.

Secondary Gain Selection Endpoint:

Individual frequency-specific gain comparison for the two different fitting strategies (*Vibe SF* and HCP fit) for each ear as measured with probe-mic real-ear measures (REM).

Secondary Preference Endpoint:

Fitting preference *Vibe SF* or HCP fit strategy. Subjects are asked which of the hearing aids they would prefer to keep using a 5-point Likert scale.

Secondary Safety Endpoint:

The number of adverse device effects (ADEs) in the time period when the subject is using the *Vibe SF* hearing aids.

Population: A minimum of 28 US subjects, within the age of 18 years and older, inexperienced or experienced hearing aid users with perceived mild-to-moderate hearing impairment. Potential subjects will be screened to confirm their bilateral sensorineural hearing loss.

Description of Sites/Facilities Enrolling Subjects: A single US University hearing aid research clinic. Potential subjects will be recruited locally by outreach at the investigator sites, local advertisements, social media advertisements and if needed professional recruiting service.

Study Duration: **Adaptive Design: IF no significant Interaction Effect**

28 Subjects: Cross-over design

Enrollment (Visit 1)	30 days	4 weeks
Field Tests	28 days (+6 days)	4 weeks
2 weeks Field Test 1 +3 days, 2 weeks Field Test 2 + 3 days		
Follow-up (Visit 2)	1 day (+7 days)	
Washout Period	5 days (+2 days)	1 week
Follow-up Visit (Visit 3)	1 day (+7 days)	
Interim analysis of nuisance parameter (interaction effect)	0 (done in parallel during Field Test 1)	0
Completion of data analysis	90 days	12 weeks

TOTAL Duration	155 days (+22 days)	25 weeks/6 months
-----------------------	---------------------	-------------------

Adaptive Design: IF significant Interaction Effect

12 Subjects: Cross-over design

Enrollment (Visit 1)	30 days	4 weeks
Field Tests	28 days (+6 days)	4 weeks
2 weeks Field Test 1 +3 days, 2 weeks Field Test 2 + 3 days		
Follow-up (Visit 2)	1 day (+7 days)	
Washout Period	5 days (+2 days)	1 week
Follow-up Visit (Visit 3)	1 day (+7 days)	
Interim analysis of nuisance parameter (interaction effect)	0 (done in parallel during Field Test 1)	0
Subtotal Duration	65 days (+22 days)	13 weeks/3 months

38 Subjects: Parallel-arm design

Enrollment (Visit 1)	30 days	4 weeks
Field Test 1	14 days (+3 days)	2 weeks
Follow-up (Visit 2)	1 day (+7 days)	
Completion of data analysis	90 days	12 weeks
Subtotal Duration	135 days (+10 days)	18 weeks/4.5 months
Grand TOTAL Duration	200 days (+32 days)	31 weeks/7.5 months

Subject Duration:

Adaptive Design: IF no Significant Interaction Effect

28 subjects

Each subject receives both treatments (cross-over design)

7 weeks total study duration on-study per subject

Adaptive Design: IF significant Interaction Effect

50 subjects:

- Before the interim analysis, 12 subjects get both treatments (cross-over design)
- After the interim analysis, 38 subjects get one treatment (parallel-arm design)

12 subjects get both treatments = 7 weeks total study duration on-study per subject

38 subjects get one treatment = 3 weeks total study duration on-study per subject

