Week 5-7
(+3 days)

Sound Quality, Speech Understanding & Satisfaction EMA Ratings
ADEs: **Vibe SF** Strategy

Visit 3
Week 8
(+7 days)
Exit**Final Assessments (completed by 12 participants)**

- APHAB aided: Field Test 2 hearing aids
- SSQ-12 aided: Field Test 2 hearing aids
- QuickSIN unaided, aided (randomized, double-blinded)
- REM aided (randomized, double blinded)
- Fitting Preference Likert scale question

Interim Analysis after 12 participants, additional 38 participants enrolled & complete up to Visit 2

Schedule of Activities (SoA)

Procedures	Screening -3 months	Enrollment/Baseline Visit 1, Week 0	Field Test 1 Week 1-2 +3 days	Study Visit 2 Week 3 +7 days	Washout Period + 2 days post Visit 2	Field Test 2 Week 4-5 + 3 days	12 subjects completed Visit 3	Study Visit 3 Day 30 + 7 day
Inclusion/Exclusion Criteria	X							
Demographic (e.g., gender)	X							
Medical history (e.g., Length of hearing loss, length of hearing aid use)	X							
Self-perceived hearing loss rating	X							
Hearing Test	X							
Informed consent	X							
Randomization		X						
APHAB unaided		X						
SSQ-12 unaided		X						
Bilateral Hearing Aid fitting:								
Silk 1X Issued, HCP fit strategy: NAL NL2 REM		(X)		(X)				
Vibe SF Hearing Aids Issued, SF strategy		(X)		(X)				
Shipment and Delivery of Field Test 2 Hearing Aids at 5 days + 2 days post Visit 2					X			
APHAB aided				X				X
SSQ-12 aided				X				X
Sound quality, speech understanding and hearing aid satisfaction EMA			X			X		
Follow-up Call: EMA data collection (+3 days Field Test 1 & 2)			X			X		
QuickSIN, unaided								X
QuickSIN, aided, hearing aid order randomized, double-blinded								X
QuickSIN, Field Test 1 device (parallel-arm design)				X*				
REM, hearing aid order randomized, double-blinded (cross-over design)								X
REM, Field Test 1 device (parallel-arm design)				X*				
Fitting Preference Likert question								X
Adverse device effect (ADE) review and evaluation		X	X	X		X		X
Complete electronic Case Report Forms (eCRFs)	X	X	X	X		X		X
Final Study Visit at Visit 3 for 28 subjects (cross-over design)								X*
Final Study Visit at Visit 2 for 38 subjects (parallel-arm design)				X*				
Final Study Visit at Visit 3 for 12 subjects (parallel-arm design)								X*
Interim Analysis: Interaction Effect Detection on 12 subjects						X		

(X): Visit 1: Device Fitting Strategy order randomly issued to subject. Visit 2: Cross Over to other Device Fitting Strategy

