9.4.1.1 DESCRIPTIVE STATISTICS

This section describes the descriptive statistics that will be provided with each analysis. The statistics depend on the type of variable (endpoint) that is analyzed. All secondary objectives involve descriptive analyses only.

Descriptive statistics of subject demographics and baseline hearing status will be tabulated. No comparisons will be made because the same subjects serve as *Vibe SF* strategy and HCP fit strategy subjects in this cross-over study.

The descriptive statistics that will be presented will depend on the data type:

- 1) Continuous data will be summarized using n, mean, SD, minimum and maximum values.
- 2) Categorical data will be summarized using frequency and percentage.
- 3) Time-to-event data will be summarized using percentages at relevant time points, along with effective sample size and the 95% confidence interval.
- 4) Frequency (count) data will be summarized as a categorical variable if there are 5 or fewer values (see #2), or as a continuous variable if there are more than 5 distinct values (see #1).

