9.4.4 SAFETY ANALYSES

It is very unlikely that any device-related adverse events (ADEs) will be reported during this NSR device study. However, those that are reported will be tabulated by severity (mild-moderate-severe), seriousness (serious or non-serious) and relatedness (related, not related).

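### The safety objective is an ADE rate for Vibe SF, but the endpoint is a count limited to time in use, with no denominator, device attribution or interval, although almost no events are expected

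*Combined protocol and SAP*

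**What the plan says.** The Synopsis (1.1) gives the secondary safety objective as "To estimate the rate of adverse device effects (ADEs) when the subject is using the" Vibe SF hearing aids. Its endpoint is "The number of adverse device effects (ADEs) in the time period when the subject is using the" Vibe SF hearing aids. The table in Section 3 has the same endpoint, phrases the objective as a rate of safety, and collects ADEs at visits and in field tests.

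Section 9.4.4 states the expectation: "It is very unlikely that any device-related adverse events (ADEs) will be reported during this NSR device study". It then says that "those that are reported will be tabulated by severity (mild-moderate-severe), seriousness (serious or non-serious) and relatedness (related, not related"). Section 9.1.2 repeats this. Neither names a denominator, an interval or a time window.

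The general rules in Section 9.4.1.1 add only a little. "Frequency (count) data will be summarized as a categorical variable if there are 5 or fewer values", and "Categorical data will be summarized using frequency and percentage". The only interval among the descriptive rules is for another data type: "Time-to-event data will be summarized using percentages at relevant time points, along with effective sample size and the 95% confidence interval".

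On capture, the Schedule of Activities row "Adverse device effect (ADE) review and evaluation" is marked at Visits 1 to 3 and both field tests, but not in the washout column. Section 8.3.4 requires all adverse events on study to be documented, with onset and relationship. Section 8.2 has subjects asked again at the Field Test 2 call and at Visit 3. Section 8.3.3.2 grades relatedness to the study intervention in general, and the ADE definition in Section 8.3.1 extends to a comparator that is a medical device.

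**The concern.** Objective, endpoint and analysis do not line up. A rate needs a denominator, and a rate estimated from very few events needs a statement of precision. The plan expects about zero events and provides for neither, so its most likely safety result is a row of zeros that a reader cannot interpret.

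The endpoint also decides what counts by calendar time on Vibe SF. A cross-over subject who has Vibe SF first goes on to a washout in which no study device is worn. An effect of Vibe SF with onset there lies outside the endpoint as worded, even if the clinician believes Vibe SF caused it. Because relatedness is not graded by device, the data would not show which device such an event belongs to. At stake is whether the safety result answers its own objective. The primary analysis is untouched.

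**Working it through.** **1. The plan's own figure.** The documents give no ADE rate, precision or detection probability. The checkable figure is the sample size that supplies the safety denominator (Section 9.2). For a one-sided paired t-test with true difference 0 and α = 0.05, power = 1 − F(t) for the noncentral t with N − 1 degrees of freedom and noncentrality (NIM/σ)√N, where t is the 95th percentile of the central t. Using the margins and SDs in the power tables:

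| Subscale | NIM | σ | N | Power in plan | Power recomputed |
|---|---|---|---|---|---|
| EC | 26 | 34.4 | 23 | 0.96892 | 0.96892 |
| RV | 28 | 36.1 | 22 | 0.96942 | 0.96942 |
| BN | 27 | 36.2 | 23 | 0.96555 | 0.96555 |

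The largest N, 23, is raised to 24 for balance, and 24 + 4 = 28 are enrolled. At 15% dropout, 28 × 0.85 = 23.8, or about 24 completers. The figure reproduces.

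**2. Candidate denominators.**
- Cross-over retained: 28 if everyone enrolled is fitted with Vibe SF, 24 if only completers count.
- Switched to parallel arms: the Vibe SF arm is 6 + 19 = 25. The 6 initial subjects who start with Silk 1X also cross to Vibe SF, giving 25 + 6 = 31 ever exposed. Section 3 collects ADEs from the initial 12 in both field tests, whereas Section 9.4.1 sets aside their post-cross-over data after a switch. The plan does not say which applies to safety.
- Section 9.3 assigns secondary objectives to the mITT population, a subset of an ITT population defined by receiving either fitting. It is therefore not a Vibe SF-exposed population.

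**3. What a zero count would mean.** With 0 of n subjects affected, the Clopper-Pearson two-sided 95% upper limit is 1 − 0.025^(1/n):

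| n | Upper limit |
|---|---|
| 24 | 1 − 0.025^(1/24) = 14.2% |
| 25 | 1 − 0.025^(1/25) = 13.7% |
| 28 | 1 − 0.025^(1/28) = 12.3% |
| 31 | 1 − 0.025^(1/31) = 11.2% |

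One affected subject in 28 gives 0.09% to 18.35%. If the rate is read per unit of time, 28 × 14 = 392 person-days with no event gives an exact Poisson upper limit of 3.689/392 = 0.94 per 100 person-days, where 3.689 = −ln 0.025.

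**4. Chance of seeing nothing.** The documents give no ADE risk, so a range is assumed. The probability of zero affected subjects is (1 − p)^n. At p = 5% it is 0.95^28 = 0.24 and 0.95^24 = 0.29. At p = 2% it is 0.98^28 = 0.57 and 0.98^24 = 0.62.

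**5. A Vibe SF effect with onset in the washout, rule by rule.**
- Recorded? Yes (8.3.4).
- Asked about? Yes, at the Field Test 2 call and Visit 3 (8.2).
- In the 9.4.4 tabulation? Yes, since that has no time window.
- In the endpoint as worded? No, because the subject is not using Vibe SF.
- Attributable to Vibe SF from the recorded relatedness? Not by any stated rule (8.3.3.2).

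**The case against.** The best defence is that capture is sound. Adverse events are recorded throughout, ADEs are defined by relation to the device rather than by onset date, and the Independent Medical Monitor reviews causality for every event (10.1.5). Section 9.1.2 asks for descriptive statistics by fitting strategy, which with 9.4.1.1 can yield a percentage. The endpoint is descriptive and untested, and anyone can compute an exact interval from a reported count.

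Most of this stands, and it rules out several stronger readings:
- A reader might infer that washout effects are lost. They are not; only the endpoint wording omits them.
- A reader might infer that they would be charged to Silk 1X. No rule does so, and there is no Silk 1X ADE endpoint to receive them.
- A reader might set the 5 to 7 washout days against the 14 days of use and read the ratio as a share of missed effects. It is only a ratio of calendar days, and it concerns only cross-over subjects who have Vibe SF first.
- Splitting ADEs by relatedness might look like an error. It is harmless redundancy, since all adverse events are collected and graded.
- No section says that zero events would mean no risk.

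What the defence does not supply is a stated denominator, attribution to a named device, or an interval. A later reader can add an interval only if the number exposed and the device responsible are reported.

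**Conclusion.** The point holds as a mismatch between a rate objective, a count endpoint limited to time in use, and a tabulation without denominator or precision. It does not hold as a failure of safety surveillance. In size, a zero result would remain compatible with a per-subject ADE risk of up to about 11% to 14% (two-sided 95%), and the plan would show none of this.

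The limits rest on these assumptions: every enrolled subject is fitted with Vibe SF (28) or only completers count (24); each subject counts once; and, after a switch, only the initial 12 have crossed over. Because enrolment continues during the interim analysis (9.4.1), more may have crossed by then, which would raise 31 and lower its limit slightly. This is an inexpensive improvement to a descriptive endpoint; no primary conclusion depends on it.

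**What to change.** 1. In 1.1 and Section 3, define the endpoint as subjects with at least one ADE that the clinician relates to Vibe SF, whatever the onset date while on study, over all subjects ever fitted with Vibe SF. In 8.3.3.2 and the eCRF, record relatedness separately for Vibe SF and Silk 1X.
2. In 9.4.4, report this proportion with an exact (Clopper-Pearson) 95% confidence interval, and state whether post-cross-over safety data count after a switch. The denominator above implies that they do (31 rather than 25).

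A calendar window from first Vibe SF fitting to the start of the next device would not work. The second device is fitted at Visit 2, then collected and shipped after the washout (8.1.4, 8.1.5). If start means fitting, the washout after Vibe SF is still excluded; for subjects who begin with Silk 1X, the washout after Silk 1X would fall inside the Vibe SF window.

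Cost: endpoint and analysis wording and a relatedness item per device, with no extra subjects or visits and no change to the sample size or primary analysis. The safety statement becomes slightly less favourable because the upper limit is shown. Attribution rests on clinical judgement that is open during field use (6.3).

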1.2 SCHEMA

ADAPTIVE DESIGN: NO INTERACTION EFFECT (Cross-over Design)

Prior to Enrollment -3 months

Total N = 28: Obtain informed consent. Screen potential participants by inclusion and exclusion criteria; obtain history, document.

Fitting Strategy

Visit 1
Enrollment
Baseline
Week 0

Vibe SF

N = 6 + 8 (cross-over design*)

HCP fit

N = 6 + 8 (cross-over design*)

Field Test 1
Week 0-2
(+3 days)Sound Quality, Speech Understanding & Satisfaction EMA Ratings
ADEs: Vibe SF StrategyVisit 2
Week 3
(+7 days)

- APHAB aided: Field Test 1 hearing aids
- SSQ-12 aided: Field Test 1 hearing aids
- Cross Over Fitting of Hearing Aids for Field Test 2: Vibe SF or Silk 1X HCP fit
- Silk 1X: HCP fitted to NAL-NL2 prescriptive target verified by REM

Cross Over Fitting Strategy

5 days Washout

Vibe SF
N = 6 + 8*HCP fit
N = 6 + 8*Field Test 2
Week 5-7
(+3 days)Sound Quality, Speech Understanding & Satisfaction EMA Ratings
ADEs: Vibe SF StrategyVisit 3
Week 8
(+7 days)
Exit

Final Assessments

- APHAB aided: Field Test 2 hearing aids
- SSQ-12 aided: Field Test 2 hearing aids
- QuickSIN unaided, aided (randomized, double-blinded)
- REM aided (randomized, double blinded)
- Fitting Preference Likert scale question

Interim Analysis after 12 participants, continue cross-over design

ADAPTIVE DESIGN: INTERACTION EFFECT DETECTED (Parallel-arm Design)**Prior to Enrollment -3 months**

Total N = 50: Obtain informed consent. Screen potential participants by inclusion and exclusion criteria; obtain history, document.

Randomize

Fitting Strategy**Vibe SF**

N = 6 + 19 (parallel-arm design)

HCP fit

N = 6 + 19 (parallel-arm design)

Visit 1
Enrollment
Baseline
Week 0

- APHAB unaided
- SSQ-12 unaided
- Fitting of Hearing Aids for Field Test 1: **Vibe SF** or **Silk 1X HCP fit**
- Silk 1X: HCP fit to NAL-NL2 prescriptive target verified by REM

Field Test 1
Week 0-2
(+3 days)

Sound Quality, Speech Understanding & Satisfaction EMA Ratings
ADEs: **Vibe SF** Strategy

Visit 2
Week 3
(+7 days)

- APHAB aided: Field Test 1 hearing aids
- SSQ-12 aided: Field Test 1 hearing aids
- Cross Over Fitting of Hearing Aids for Field Test 2: **Vibe SF** or **Silk 1X HCP fit**
- Silk 1X: HCP fitted to NAL-NL2 prescriptive target verified by REM
- **FINAL VISIT for parallel arm design: 38 participants**
- **QuickSIN & REM aided: Field Test 1 hearing aids (only for 38 participants parallel-arm design)**

Cross Over Fitting Strategy**Vibe SF**
N = 65 days
Washout**HCP fit**
N = 6**Field Test 2**
Week 5-7
(+3 days)

Sound Quality, Speech Understanding & Satisfaction EMA Ratings
ADEs: **Vibe SF** Strategy

Visit 3
Week 8
(+7 days)
Exit**Final Assessments (completed by 12 participants)**

- APHAB aided: Field Test 2 hearing aids
- SSQ-12 aided: Field Test 2 hearing aids
- QuickSIN unaided, aided (randomized, double-blinded)
- REM aided (randomized, double blinded)
- Fitting Preference Likert scale question

Interim Analysis after 12 participants, additional 38 participants enrolled & complete up to Visit 2

Schedule of Activities (SoA)

Procedures	Screening -3 months	Enrollment/Baseline Visit 1, Week 0	Field Test 1 Week 1-2 +3 days	Study Visit 2 Week 3 +7 days	Washout Period + 2 days post Visit 2	Field Test 2 Week 4-5 + 3 days	12 subjects completed Visit 3	Study Visit 3 Day 30 + 7 day
Inclusion/Exclusion Criteria	X							
Demographic (e.g., gender)	X							
Medical history (e.g., Length of hearing loss, length of hearing aid use)	X							
Self-perceived hearing loss rating	X							
Hearing Test	X							
Informed consent	X							
Randomization		X						
APHAB unaided		X						
SSQ-12 unaided		X						
Bilateral Hearing Aid fitting:								
Silk 1X Issued, HCP fit strategy: NAL NL2 REM		(X)		(X)				
Vibe SF Hearing Aids Issued, SF strategy		(X)		(X)				
Shipment and Delivery of Field Test 2 Hearing Aids at 5 days + 2 days post Visit 2					X			
APHAB aided				X				X
SSQ-12 aided				X				X
Sound quality, speech understanding and hearing aid satisfaction EMA			X			X		
Follow-up Call: EMA data collection (+3 days Field Test 1 & 2)			X			X		
QuickSIN, unaided								X
QuickSIN, aided, hearing aid order randomized, double-blinded								X
QuickSIN, Field Test 1 device (parallel-arm design)				X*				
REM, hearing aid order randomized, double-blinded (cross-over design)								X
REM, Field Test 1 device (parallel-arm design)				X*				
Fitting Preference Likert question								X
Adverse device effect (ADE) review and evaluation		X	X	X		X		X
Complete electronic Case Report Forms (eCRFs)	X	X	X	X		X		X
Final Study Visit at Visit 3 for 28 subjects (cross-over design)								X*
Final Study Visit at Visit 2 for 38 subjects (parallel-arm design)				X*				
Final Study Visit at Visit 3 for 12 subjects (parallel-arm design)								X*
Interim Analysis: Interaction Effect Detection on 12 subjects						X		

(X): Visit 1: Device Fitting Strategy order randomly issued to subject. Visit 2: Cross Over to other Device Fitting Strategy

X*: Adaptive design: detection analysis of significant interaction effect impacting sample size and study design (cross-over vs parallel-arm design)

